STUDY PROTOCOL

Official Title

A Randomized Controlled Trial on Shared Decision-Making for Colorectal Cancer Screening
Among High-Risk First-Degree Relatives Aged 40–49

Protocol ID

202509053RINA

NCT Number

Pending

Document Type

Study Protocol

Version Date

23 October 2025

Sponsor / Coordinating Center

National Taiwan University Hospital

Principal Investigator

[name], PhD
National Taiwan University Hospital

A Randomized Controlled Trial on Shared Decision-Making for Colorectal Cancer Screening Among High-Risk First-Degree Relatives Aged 40–49

1. Background

Colorectal cancer (CRC) remains a major global health challenge. According to GLOBOCAN 2020, CRC is the third most commonly diagnosed cancer worldwide and the second leading cause of cancer-related death, with more than 1.9 million new cases and over 900,000 deaths annually.

Most CRC develops through a gradual progression from benign adenomatous polyps to invasive carcinoma over several years. Screening programs are effective because they detect and remove precancerous lesions or detect cancer at an earlier stage when treatment is more effective.

Individuals with a first-degree relative (FDR) diagnosed with CRC—defined as a biological parent, sibling, or child—have significantly increased risk of developing CRC. International evidence shows that individuals with an affected FDR have approximately 2.25 times the risk of CRC compared with those without family history. If the relative was diagnosed before age 45, the risk increases to approximately 3.87 times, and if more than two FDRs are affected, the risk increases to approximately 4.25 times.

Guidelines from the US Multi-Society Task Force and the American College of Gastroenterology recommend that individuals with a first-degree relative diagnosed with CRC before age 60 begin screening at age 40 or 10 years earlier than the youngest diagnosis in the family.

Despite these recommendations, screening uptake among high-risk individuals aged 40–49 remains low. Studies suggest screening rates in this population are only around 31–40%. At the same time, the incidence of CRC in individuals younger than 50 has been increasing in recent years, highlighting an urgent public health concern.

Shared decision-making (SDM) is a patient-centered approach in which clinicians and patients collaborate to make healthcare decisions based on clinical evidence and patient preferences. SDM may reduce barriers to CRC screening by improving knowledge, addressing misconceptions, and aligning screening options with patient values.

Decision aids are commonly used tools in SDM. These materials present balanced information about screening options, including colonoscopy and fecal immunochemical testing (FIT), allowing patients to compare benefits, risks, and procedures.

This trial proposes that a structured SDM intervention that explicitly offers both colonoscopy and FIT as screening options may increase screening uptake among high-risk individuals compared with the standard approach of direct colonoscopy referral.

2. Study Objectives and Hypotheses

Primary Objective

The primary objective of this study is to evaluate whether a structured shared decision-making intervention improves colorectal cancer screening uptake among individuals aged 40–49 with a first-degree relative diagnosed with CRC compared with standard care.

Primary Hypothesis

Participants assigned to the SDM intervention will have a higher screening completion rate within three months after randomization compared with those assigned to standard care.

Secondary Objectives

- Evaluate participant satisfaction with the decision-making process and care received.
- Assess the quality of the SDM process using validated questionnaires.
- Examine screening modality choices (colonoscopy vs FIT).
- Evaluate detection rates of colorectal neoplasia, including adenoma, advanced adenoma, and colorectal cancer.

3. Study Design and Methodology

Overall Design

This study is a two-arm parallel randomized controlled trial. Participants will be randomized in a 1:1 ratio to either the SDM intervention group or the standard care group.

Study Setting

Participants will be recruited from multiple medical centers in Taiwan including hospitals in northern, central, and southern regions.

Participant Eligibility

Inclusion Criteria:

- Age 40–49 years
- At least one first-degree relative diagnosed with CRC
- Ability to understand study procedures and provide written informed consent

Exclusion Criteria:

- Personal history of CRC or inflammatory bowel disease

- Symptoms requiring diagnostic evaluation rather than screening
- Medical conditions contraindicating colonoscopy
- Colonoscopy within the past three years

4. Outcome Measures

Primary Outcome

Colonoscopy uptake within three months after randomization.

Secondary Outcomes

- Patient satisfaction measured using the Shared Decision Making Questionnaire (SDM- Q- 9)
- Screening modality selection among participants in the SDM group
- Detection rates of colorectal neoplasia

5. Data Collection and Management

All study data will be collected and managed using REDCap (Research Electronic Data Capture), a secure web- based platform designed for research data management. Data will be entered into electronic case report forms by trained research staff.

6. Study Duration and Coordination

The study is expected to run from September 1, 2025 to December 31, 2026. The coordinating center will be National Taiwan University Hospital. Collaboration will involve multiple hospitals across Taiwan, with principal investigators at each participating center responsible for local coordination.

7. Ethical Considerations

This study will follow the ethical principles outlined in the Declaration of Helsinki and Good Clinical Practice guidelines. Approval will be obtained from the Institutional Review Boards of all participating institutions prior to study initiation.

Informed consent will be obtained from all participants before any study procedures are performed. Participant confidentiality will be strictly maintained through the use of unique study identification numbers and secure data storage systems.

8. Potential Risks and Benefits

Risks associated with participation are minimal and primarily related to time commitment. Risks associated with colonoscopy include bleeding, perforation, and sedation- related complications. FIT screening may produce false- positive or false- negative results.

Potential benefits include increased knowledge about CRC screening and the opportunity to participate in informed decision-making regarding screening options.

9. Expected Outcomes

This study aims to generate evidence regarding the effectiveness of shared decision-making strategies in increasing CRC screening uptake among high-risk populations. If effective, the intervention may inform future screening policies and clinical guidelines and contribute to improved CRC prevention strategies.

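### The primary outcome counts colonoscopy only, while the primary objective and hypothesis concern screening that includes FIT, so the stated hypothesis is not tested

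*Protocol*

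**What the plan says.** Section 2, Primary Objective, is to "evaluate whether a structured shared decision-making intervention improves colorectal cancer screening uptake among individuals aged 40–49". The Primary Hypothesis follows: "Participants assigned to the SDM intervention will have a higher screening completion rate within three months after randomization". Neither restricts the screening test.

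The last paragraph of the Background, directly before the objectives, states the rationale: "a structured SDM intervention that explicitly offers both colonoscopy and FIT as screening options may increase screening uptake among high-risk individuals". The comparator given there is the usual practice of referring people straight to colonoscopy. A secondary objective in section 2 treats colonoscopy and FIT as the two modality choices. Section 9 again describes the aim as raising uptake of CRC screening.

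Section 4, Primary Outcome, reads: "Colonoscopy uptake within three months after randomization". FIT is not mentioned there. The secondary outcomes are the SDM-Q-9, neoplasia detection, and "Screening modality selection among participants in the SDM group".

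**The concern.** The hypothesis and the outcome share the same three-month window, so they are two definitions of one primary comparison, and they differ in which test counts. The intervention is expected to raise uptake partly by offering FIT alongside colonoscopy. Under section 4, someone who takes up that offer, completes FIT and has no colonoscopy in the window is counted with those who were not screened at all.

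Two things are at stake. First, the part of the intervention meant to raise screening can lower the measured outcome, so a programme that works as hypothesised could be reported as ineffective or worse than direct referral. Second, with two definitions in one document, the choice between them could be made after results are known. Section 9 expects the findings to inform screening policy and guidelines.

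**Working it through.** **1. Text check.** The protocol states no sample size, significance level, power or effect size, so there is no planned figure to reproduce. The contradiction rests on the text.

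| Place in protocol | What is to be raised or counted | Test |
|---|---|---|
| Background, last paragraph | screening uptake | colonoscopy and FIT both named |
| Section 2, Primary Objective | CRC screening uptake | not restricted |
| Section 2, Primary Hypothesis | screening completion, three months | not restricted |
| Section 4, Primary Outcome | uptake, three months | colonoscopy only |
| Section 4, modality selection | choice of test | SDM arm only |
| Section 9 | CRC screening uptake | not restricted |

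No row of section 4 gives a between-arm comparison of completion by either test.

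**2. Illustration of size.** Inputs:

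- Control uptake pC = 31–40%. This is the Background's figure for screening rates in this population, borrowed here. The protocol does not state it as a control-arm assumption. All control screening is assumed to be colonoscopy.
- True gain in screening by either test, d = 10, 15 or 20 points (assumed), so pS = pC + d.
- f = share of screened SDM participants who complete FIT and have no colonoscopy in the window (varied).

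Measured colonoscopy difference = pS(1 − f) − pC. It is zero when f = d / pS.

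| pC | d = 10 | d = 15 | d = 20 |
|---|---|---|---|
| 31% | 10/41 = 24.4% | 15/46 = 32.6% | 20/51 = 39.2% |
| 35.5% (midpoint) | 10/45.5 = 22.0% | 15/50.5 = 29.7% | 20/55.5 = 36.0% |
| 40% | 10/50 = 20.0% | 15/55 = 27.3% | 20/60 = 33.3% |

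The break-even share therefore runs from 20% to 39%, and it does not depend on sample size.

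**3. Midpoint example** (pC = 35.5%, pS = 50.5%, true gain 15 points):

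| f | SDM colonoscopy = 50.5 × (1 − f) | Measured difference, points |
|---|---|---|
| 0% | 50.50% | +15.00 |
| 10% | 45.45% | +9.95 |
| 20% | 40.40% | +4.90 |
| 30% | 35.35% | −0.15 |
| 40% | 30.30% | −5.20 |

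**4. Power, illustrative only.** Assume a two-sided 5% test, 1:1 allocation, and n per arm set to give 80% power for the any-test difference. With p̄ the mean of the two rates and Δ their difference, power = Φ{[Δ − 1.96·√(2p̄(1 − p̄)/n)] / √[(p1(1 − p1) + p2(1 − p2))/n]}. At the midpoint n = 170 per arm. Switching to colonoscopy only, power falls to 46% at f = 10% and 15% at f = 20%. Over the nine combinations in step 2 (n from 94 to 388 per arm), power at f = 10% ranges from 29% to 56%. At f = 20% it is at most 29%, and in one combination (40%, gain 10) the true colonoscopy difference is already zero.

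**5. Sensitivity to control-arm FIT.** If a share g of screened controls also use FIT only, break-even becomes f = 1 − (pC/pS)(1 − g). At the midpoint with g = 10% (assumed): 1 − (35.5/50.5) × 0.90 = 36.7%, against 29.7% at g = 0. The problem shrinks but remains.

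**The case against.** The strongest reply is that colonoscopy uptake is a legitimate endpoint. A randomised comparison of it validly estimates the effect on colonoscopy, and parts of the protocol are built around colonoscopy: the exclusion criteria cover recent colonoscopy and contraindications to it, but not recent FIT. That stands as far as it goes. The outcome is not invalid in itself; it answers a different question from the one in section 2. A reader might call it biased against the intervention, but that holds only if completion by either test is the target. Misaligned is the accurate word.

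Three further inferences are tempting and go too far.

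- *That every SDM participant who completes FIT is scored as a failure.* Someone who has both FIT and a colonoscopy within three months, for example after a positive FIT, counts as a success. Only FIT-only completers are lost.
- *That the loss occurs in one arm only.* Standard care is described as direct colonoscopy referral, but nothing says controls cannot obtain FIT. Imbalance is likely from the design as described; it is not established.
- *That a definite loss of power, or a definite chance of a significant result in the wrong direction, can be quoted.* With 35% of controls against 25% colonoscopy in the SDM arm (50% screened, half by FIT only), the chance of a significant result favouring control is about 34% at 100 per arm, 59% at 200 and 87% at 400. With no sample size in the protocol, none of these describes this trial.

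It is also fair to say that the objective and hypothesis do not literally add the words colonoscopy or FIT. The adjoining rationale and the modality objective supply that meaning, and no text points the other way. Nor can the matter be left to an SAP: the protocol already fixes the primary event, and an SAP would have to override either section 2 or section 4.

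**Conclusion.** The contradiction holds and nothing in the protocol resolves it. As written, the primary outcome does not test the primary hypothesis, no other listed outcome does so, and a true rise in screening could be reported as no benefit or as harm.

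The direction follows from FIT being offered, as described, in the SDM arm only. The size is conditional: the 20–39% break-even share rests on a borrowed background rate, an assumed gain of 10–20 points and no FIT-only screening among controls. The power figures are illustrative at best. The finding does not depend on them, because the mismatch is in the definitions. It should be corrected before outcome data are seen.

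**What to change.** Reconcile sections 2 and 4. The version that fits the stated objective, hypothesis and section 9 is a primary outcome of completed CRC screening, meaning colonoscopy performed or FIT returned with a valid result, within three months of randomisation and ascertained the same way in both arms. Colonoscopy uptake by arm then becomes a secondary outcome. The registry entry should carry the same wording; the title page shows the NCT number as pending.

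If colonoscopy uptake is the intended target, section 4 can stand, but the primary objective and hypothesis must be restated as colonoscopy uptake. The sponsor has to say which was meant.

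The cost is a short amendment, with approval from the review boards of the participating institutions. FIT completion must also be recorded among controls, since section 4 now lists modality for the SDM group only. The planned start (1 September 2025) precedes the version date (23 October 2025), so enrolment may have begun, and early controls may need FIT status collected afterwards. Whether the change affects the number of participants cannot be judged without a stated sample size. The drawback is that the primary outcome would count FIT and colonoscopy equally; the secondary colonoscopy comparison keeps that difference visible.

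### The SDM-Q-9 is labelled as the satisfaction measure, which leaves satisfaction with care unmeasured and the separate SDM-quality objective without a listed outcome

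*Protocol*

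**What the plan says.** The Protocol, Section 2 (Secondary Objectives), lists two questionnaire-type aims as separate bullets. The first is "Evaluate participant satisfaction with the decision-making process and care received". The second is "Assess the quality of the SDM process using validated questionnaires".

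Section 4 (Secondary Outcomes) lists three items. Only one is a questionnaire: "Patient satisfaction measured using the Shared Decision Making Questionnaire", with the SDM-Q-9 given as its abbreviation. The other two are "Screening modality selection among participants in the SDM group" and the detection of neoplasia. No other questionnaire is named anywhere in the Protocol.

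On what the arms receive, Section 1 describes "a structured SDM intervention that explicitly offers both colonoscopy and FIT as screening options may increase screening uptake among high-risk individuals", set against a comparator in the words "compared with the standard approach of direct colonoscopy referral". The Protocol does not say which arms complete the SDM-Q-9 or when, and it does not reproduce the items.

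**The concern.** The Protocol itself treats satisfaction and SDM quality as different things, because it gives each its own objective. Section 4 then assigns the one named instrument to satisfaction, although its title describes a shared decision-making questionnaire. Following the plan as written, a score for the decision process would be reported under the heading of satisfaction.

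Two things are at stake. First, part of the satisfaction objective cannot be answered from the listed outcomes, and an analysis plan cannot supply data that were not collected. Second, if the arms are compared on this score, the result is open to misreading. The intervention is meant to make the decision more shared, so a higher score in that arm would be the expected sign that it worked as a process. Readers of a results table would see it as patients being more satisfied.

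**Working it through.** No arithmetic applies: the Protocol gives no figure that bears on this point. The check is to map each secondary objective in Section 2 to the outcomes and instruments in Section 4.

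| Objective (Section 2) | Listed outcome (Section 4) | Instrument | Result |
|---|---|---|---|
| Satisfaction: decision-process part | Patient satisfaction | SDM-Q-9 | Indirect at best |
| Satisfaction: care part | Patient satisfaction, in label only | None that addresses care | Not measured |
| Quality of the SDM process | None | None assigned, though the SDM-Q-9 fits by name | No listed outcome |
| Modality choice | Modality selection, SDM group | Not a questionnaire | Covered for that group; not relevant here |
| Neoplasia detection | Detection rates | Not a questionnaire | Covered; not relevant here |

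1. **Count.** Two objectives call for a questionnaire, and one questionnaire outcome is listed. Instruments for satisfaction with care: 0. Outcomes labelled as SDM quality: 0.

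2. **Which objective the instrument fits.** The evidence within the document is the instrument's name and the existence of a separate objective on SDM quality. Both point to the process objective. This inference does not need the items.

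3. **What a between-arm comparison would show.** Suppose both arms complete the scale. One arm receives structured SDM with two tests on offer, and the other is referred directly for colonoscopy. A score of how far the decision was shared would be expected to favour the first arm if the intervention is delivered as intended. That difference is compatible with greater, equal or lower satisfaction with care, so it does not by itself establish any of them.

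4. **What happens if only the SDM arm completes it.** Then there is no between-arm comparison under the satisfaction label at all. The modality outcome is already restricted to that arm, so this reading is open. The missing measure for care remains in either case.

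**The case against.** The strongest reply is that the satisfaction objective explicitly includes the decision-making process, and a shared decision-making questionnaire plausibly touches that part. This stands in part: it would be too broad to say that the satisfaction objective is not measured at all. It does not help the care part, and it leaves SDM quality without an outcome.

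A second reply is that the gap for SDM quality is one of labelling, since the data suited to that objective would be collected anyway. That is fair, and it is why relabelling is enough for that half. The plural in "Assess the quality of the SDM process using validated questionnaires" also leaves room for further instruments in documents not shown, but it does not change what Section 4 lists.

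A reader might go further and infer that the SDM-Q-9 must differ between arms by construction. The Protocol does not support this. It does not say that both arms complete the scale, it does not describe counselling in the control arm beyond direct referral, and being offered two options does not guarantee that a participant feels the decision was shared. The expected direction can be anticipated, but the size is an empirical question. For the same reason, a difference should not be dismissed as showing delivery of the intervention and nothing else, because perceived SDM quality is an objective in its own right.

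A reader might also infer that the trial will make a false claim about satisfaction. The text shows only that such a claim would be unsupported. Participants may in fact be more satisfied, and the Protocol states no hypothesis or reporting plan for satisfaction.

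**Conclusion.** The concern holds as a misassigned measure. Of two questionnaire objectives, one (SDM quality) has no listed outcome. The other (satisfaction) has no measure for its care part and at most an indirect one for its process part. Confidence in this mapping is high because it rests on the Protocol's own wording.

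The between-arm point is conditional on both arms completing the SDM-Q-9. It also assumes, from the name of the instrument and the separate process objective, that the score reflects how the decision was made.

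The matter should be corrected but is not critical. It concerns secondary outcomes and leaves the primary outcome, the randomization and the primary analysis untouched. It does change what the trial may conclude about satisfaction.

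**What to change.** In Section 4, rename the SDM-Q-9 outcome as perceived quality of the SDM process. This gives the second objective its outcome at no cost beyond wording.

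Then choose one of two routes for satisfaction:

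- **Keep the objective.** Add a brief satisfaction measure that covers care and makes sense to participants in both arms, given in both arms at the same time point. The cost is a few extra items in the existing REDCap form and a small added burden on participants.
- **Drop the objective.** Delete it from Section 2 and draw no conclusion about satisfaction from the SDM-Q-9. This costs wording only, but the trial gives up the question.

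The same edit should state which arms complete the SDM-Q-9 and when, so that a reader can tell whether a between-arm comparison is intended. If the first route is chosen, the change is best made before many participants have passed the assessment point, since satisfaction data not collected from them may be unrecoverable. Section 6 gives a start of September 1, 2025, and the Protocol is dated 23 October 2025; it does not state whether enrolment has begun.

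### Modality is an outcome only as selection in the SDM arm and completed FIT is an outcome in neither arm, so the listed outcomes cannot separate added screening from substitution.

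*Protocol*

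**What the plan says.** Four statements in the protocol bear on this point.

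- Section 4, Secondary Outcomes, lists modality as "Screening modality selection among participants in the SDM group".
- Section 2, Secondary Objectives, states the corresponding aim without naming an arm: "Examine screening modality choices (colonoscopy vs FIT").
- Section 4, Primary Outcome, is "Colonoscopy uptake within three months after randomization", again with no arm restriction.
- Section 2, Primary Hypothesis, concerns a different quantity: "Participants assigned to the SDM intervention will have a higher screening completion rate within three months after randomization".

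The end of Section 1 describes the contrast under test. The intervention "explicitly offers both colonoscopy and FIT as screening options may increase screening uptake among high-risk individuals compared with the standard approach of direct colonoscopy referral". FIT is therefore explicitly on offer in the SDM arm, and the comparator is referral for colonoscopy. Completed FIT does not appear among the outcomes in Section 4 for either arm.

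**The concern.** What distinguishes the two arms is an explicit offer of FIT alongside colonoscopy. If more people are screened under SDM, the reader will want to know whether they are people who would otherwise have had no test, or whether some of the FIT use stands in for colonoscopy that would have happened after direct referral. Answering that takes the test completed, in both arms. An outcome confined to one arm gives no randomised comparison, and an outcome that records selection does not show whether the selected test was done. FIT obtained by control participants is not a listed outcome either.

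The stakes are interpretive. Section 9 hopes that the results will inform screening policy and guidelines. For that purpose the net change in any screening and the net change in colonoscopy are both needed, and they need not point the same way.

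**Working it through.** The protocol gives no sample size, effect size or assumed control rate, so there is no design figure to reproduce. The check is whether the quantities of interest can be obtained from the outcomes listed in Section 4.

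**Identity.** Classify each randomised participant at three months as colonoscopy, FIT only, or neither. Then, SDM minus control:

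difference in any screening = difference in colonoscopy + difference in completed FIT without colonoscopy.

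Both terms on the right are needed to say how much screening was added and how much colonoscopy was lost or gained.

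**Inputs.** All rates below are assumed for illustration. The control colonoscopy rate of 35% is borrowed from the Section 1 background figure for screening ("Studies suggest screening rates in this population are only around 31–40" percent), and the range 31% to 40% is carried through. The protocol does not present that figure as a design assumption. Control FIT is set to 0%.

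**Reading A: the primary endpoint is colonoscopy uptake (Section 4).** Assume SDM colonoscopy of 25%, with a further 40% of the SDM arm selecting FIT and having no colonoscopy.

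- Colonoscopy difference: 25 - 35 = -10 points (25 - 31 = -6; 25 - 40 = -15). This is observed.
- Let c be the proportion of FIT selectors who complete the test. SDM any screening = 25 + 40c, which runs from 25% (c = 0) to 65% (c = 1). No listed outcome gives c.

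| Control rate | Any-screening difference at c = 0 | Any-screening difference at c = 1 |
|---|---|---|
| 31% | 25 - 31 = -6 | 65 - 31 = +34 |
| 35% | 25 - 35 = -10 | 65 - 35 = +30 |
| 40% | 25 - 40 = -15 | 65 - 40 = +25 |

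The same listed results are compatible with a loss or a large gain in any screening. Each percentage point of FIT-only use among controls would lower both ends by one point, and that use is not a listed outcome.

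**Reading B: the primary endpoint is any screening (Section 2).** Assume 35% of controls are screened, all by colonoscopy, and 50% of the SDM arm are screened. The headline difference is 50 - 35 = +15 points. Let f be the share of screened SDM participants who had FIT only. SDM colonoscopy = 50 × (1 - f).

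- f = 0.2: 50 × 0.8 = 40%, so the colonoscopy difference is 40 - 35 = +5 points.
- f = 0.5: 50 × 0.5 = 25%, so the colonoscopy difference is 25 - 35 = -10 points.

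The headline is identical in both cases. Selection in the SDM arm does not supply f, which depends on completion, and it says nothing about controls.

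**Result.** Under each reading, one term of the identity is outside the listed outcomes: the FIT term under A, the split between colonoscopy and FIT under B.

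**The case against.** The strongest objection is that Section 4 already makes colonoscopy uptake the primary outcome, with no arm restriction, in a trial randomised 1:1. A net fall in colonoscopy under SDM would then be the primary result. This stands. A reader might infer from the SDM-only modality outcome that the trial could not detect displacement of colonoscopy at all, and Section 4 does not support that. It also means that the +15-point example applies only under the Section 2 reading; under Section 4 the two scenarios would show as +5 and -10. What survives is that a fall in colonoscopy alone cannot distinguish people who completed FIT instead from people who completed nothing.

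A second objection is that only the SDM arm is explicitly offered a choice, so describing selection there is reasonable. That is fair for a descriptive item. It does not explain why the test completed is not compared between arms, or why the outcome is narrower than its own objective.

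A third is that tables by test type belong in a statistical analysis plan, which is not at hand. Their layout does. But here the protocol itself states the outcome and restricts it, and an analysis plan cannot recover FIT completion that was not collected.

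Finally, a reader might infer either that control-arm FIT is not recorded, or that test type must already be recorded in both arms in order to score the primary outcome. The documents support neither. Section 5 does not list the items on the case report forms, and scoring colonoscopy uptake requires only colonoscopy data. The supportable statement is that completed FIT is not a listed outcome in either arm.

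**Conclusion.** The point holds in a limited form and should be corrected. The modality outcome is narrower than its objective, both in arm and in measuring selection rather than completion, and completed FIT is an outcome nowhere. As listed, the outcomes do not give the between-arm screening completion rate that the primary hypothesis concerns, and they do not separate added screening from substitution.

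Under the Section 4 endpoint the any-screening difference is left open over a width of 40 points, which is simply the assumed proportion selecting FIT; a smaller proportion would narrow it in step. Under the Section 2 endpoint the colonoscopy difference behind one headline can change sign. These sizes rest entirely on assumed rates. The structural gap does not.

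The root is that the Section 2 hypothesis and the Section 4 primary outcome name different endpoints. Reconciling them is necessary but does not close the gap, because one term is missing whichever is chosen.

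**What to change.** Replace the Section 4 modality outcome with: *Screening test completed within three months (colonoscopy / FIT only / none) in both arms, all randomised participants.*

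- Report the between-arm differences in any screening and in colonoscopy, each with a 95% CI, side by side. FIT use in the control arm then appears in the same table.
- Keep stated modality preference in the SDM arm as a descriptive item.
- Reconcile the Section 2 primary hypothesis with the Section 4 primary outcome, so that one endpoint is named as primary throughout.
- State how a participant with both tests is counted. The protocol does not say whether colonoscopy after a positive FIT counts as colonoscopy uptake, and if it does, the displacement estimate is blurred.

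The cost is revised outcome wording, a FIT-completion field on the case report form in both arms, and one extra table. No design figure changes, since the protocol states none. The field needs to be in place while data are being collected.
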